7.1.1.1 Prior derivation

For the current trial, limited information about PD-1 from human data was available (Phase I Study of Pembrolizumab [MK-3475; Anti-PD-1 Monoclonal Antibody] in Patients with Advanced Solid Tumours [[R16-2024](#)]). PD-1 is considered as a well-tolerated treatment with low DLT rate. Therefore, the 2 mixture components were established as follows:

1. A weakly informative prior was derived to reflect a priori assumption that the median DLT rate at the starting dose of 80 mg would equal 0.001%, and the median DLT rate at 3200 mg would equal 30%. This yields $\mu_1 = (-4.855, 1.062)$. The standard deviations were set such that large uncertainty about the parameter means is reflected, and the correlation was set to 0, thus yielding $\sigma_{1,11} = 2$, $\sigma_{1,22} = 1$ and $\rho_1 = 0$, respectively. The prior weight ϕ_1 for the first component was chosen as 0.9.
2. A high-toxicity weakly informative prior was derived to reflect the case that the compound would be much more toxic than expected. For this prior component, it was assumed that the median DLT rate at 80 mg would equal 5%, and the median DLT at 3200 mg would equal 70%. These assumptions yield $\mu_2 = (-0.578, 0.028)$. The standard deviations and correlations were set identical to the weakly informative prior, i.e. $\sigma_{2,11} = 2$, $\sigma_{2,22} = 1$ and $\rho_2 = 0$, respectively. The prior weight ϕ_2 for the second component was chosen as 0.1.

A summary of the prior distribution is provided in [Table 7.1.1.1: 1](#). Additionally, the prior probabilities of DLT at different doses, as well as the corresponding probability of under-, targeted and overdosing, are shown in [Table 7.1.1.1: 2](#). Graphically, the prior medians with accompanying 95% credible intervals are shown in [Figure 7.1.1.1: 1](#). As can be seen from both the table and the figure, the prior medians of the DLT probabilities are all quite low for the selected doses in the range of 80 mg to 800 mg which is in-line with the prior medians derived from the weakly informative prior, and the uncertainty around the medians is large, showing the low amount of information this prior provides. This is also supported by the prior sample size, i.e., the information contained in the prior. This is approximately equal to 1.35 patients. A detailed evaluation of the model using hypothetical data scenarios and operating characteristics is provided in the statistical appendix (see [Appendix 10.5](#)).

Table 7.1.1.1: 1 Summary of prior distribution

Prior Component	Mixture Weight	Mean vector	Std Dev vector	Correlation
1: Weakly Informative Prior	0.9	(-4.855, 1.062)	(2.000, 1.000)	0.000
2: High Tox	0.1	(-0.578, 0.028)	(2.000, 1.000)	0.000

Table 7.1.1.1: 2 Prior probabilities of DLTs at selected doses

Dose	Probability of true DLT rate in			Mean	Std Dev	Quantiles		
	[0–0.16)	[0.16–0.33)	[0.33–1]			2.5%	50%	97.5%
Mg	[0–0.16)	[0.16–0.33)	[0.33–1]	Mean	Std Dev	2.5%	50%	97.5%
80	0.970	0.012	0.019	0.018	0.090	0	0	0.218
160	0.961	0.015	0.024	0.023	0.103	0	0	0.319
240	0.953	0.017	0.029	0.028	0.113	0	0	0.398
320	0.946	0.020	0.034	0.033	0.122	0	0.001	0.456
480	0.930	0.026	0.044	0.043	0.139	0	0.002	0.56
640	0.912	0.034	0.054	0.055	0.154	0	0.004	0.645
800	0.881	0.049	0.070	0.075	0.172	0	0.01	0.727

Median (95% Crl)

[figure not shown]

Figure 7.1.1.1: 1

Prior medians and 95% credible intervals

7.1.1.2 Statistical model assessment

The model was assessed using 2 different metrics:

1. Hypothetical data scenarios: for various potential data constellations as they could occur in the actual trial, the maximal doses allowed in the next cohort by the model are investigated. Data scenarios thus provide a way to assess the ‘on-study’ behaviour of the model.
2. Simulated operating characteristics: these illustrate for different assumed true dose-toxicity relationships, how often a correct dose would be declared as MTD by the model. They are a way to assess the ‘long-run’ behaviour of the model.

In summary, the model showed very good behaviour as assessed by these metrics. More details can be found in Appendix 10.5. The simulations for scenarios and operating characteristics were produced using RStudio version 0.98.507.

7.1.2 Statistical design – Phase Ib (dose expansion)

The Phase Ib (dose-expansion) portion of the trial will recruit approximately 130 patients with selected locally advanced or metastatic cancers at the dose and schedule recommended by the SRC.

The analyses of the safety and efficacy for this portion of the trial will be descriptive and exploratory in nature. Additional analysis may be applied to evaluate the robustness of the efficacy results. More details will be specified in the TSAP.

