Clinical Trial Protocol

Document Number:		c09063095-08
EudraCT No.:	2017-005043-33	
BI Trial No.:	1381.1	
BI Investigational Product:	BI 754091 (ezabenlimab)	
Title:	An open-label, Phase I trial to determine the maximum-tolerated dose and investigate safety, pharmacokinetics, and efficacy of BI 754091 in patients with advanced solid tumours	
Lay Title:	A trial to find and investigate a safe dose of a new substance (BI 754091) for patients with solid tumours	
Clinical Phase:	Phase I	
Physician		
Trial Clinical Monitor:	Phone: [REDACTED] Fax: [REDACTED]	
Coordinating Investigator		
Status:	Final protocol (revised protocol [based on global amendment 7])	
Version and Date:	Version: 8.0	Date: 07 Mar 2023
Page 1 of 144		
Proprietary confidential information. © 2023 Boehringer Ingelheim International GmbH or one or more of its affiliated companies. All rights reserved. <small>THIS DOCUMENT MAY NOT - IN FULL OR IN PART - BE PASSED ON, REPRODUCED, PUBLISHED OR OTHERWISE USED WITHOUT PRIOR WRITTEN PERMISSION.</small>		

CLINICAL TRIAL PROTOCOL SYNOPSIS

Name of company:		Boehringer Ingelheim	
Name of finished product:		N.A.	
Name of active ingredient:		BI 754091	
Protocol date: 22 Sep 2016	Trial number: 1381.1		Revision date: 07 March 2023
Title of trial:	An open-label, Phase I trial to determine the maximum-tolerated dose and investigate safety, pharmacokinetics, and efficacy of BI 754091 in patients with advanced solid tumours		
Investigator			
Clinical phase:	I		
Objectives:	
Phase Ia Dose Escalation: To determine the maximum-tolerated dose (MTD) and the recommended Phase 2 dose (RP2D) and investigate the safety, pharmacokinetics (PK), biomarkers, and efficacy of BI 754091 in patients with advanced and/or metastatic solid tumours
 
Phase Ib Dose Expansion: To further evaluate the safety, the PK profile, biomarkers, and efficacy of the RP2D in 4 cohorts of patients with selected advanced and/or metastatic cancers
		
Methodology:	
Phase Ia Dose Escalation: Open-label, single arm, dose escalation (consecutive cohorts of escalating doses of BI 754091), Bayesian Logistic Regression Model (BLRM) with overdose control
 
Phase Ib Dose Expansion: Open-label, 4 dose-expansion cohorts
		
No. of patients:	Approximately 145 patients, depending on dose-escalation results		

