Total entered:	
Phase Ia Dose Escalation: approximately 15 patients
 
Phase Ib Dose Expansion at the RP2D: 4 cohorts of approximately 30-40 patients each
		
Each treatment:	All patients participating in any part of this trial will receive BI 754091.		

Name of company:	Boehringer Ingelheim	
Name of finished product:	N.A.	
Name of active ingredient:	BI 754091	
Protocol date: 22 Sep 2016	Trial number: 1381.1	Revision date: 07 March 2023
Diagnosis:	
Phase Ia Dose Escalation: Patients with a confirmed diagnosis of advanced, unresectable, and/or metastatic solid tumours.
 
Phase Ib Dose Expansion: advanced and/or metastatic cancers including tumours with specific histology/tumour types and/or specific genetic profiles as specified in the following cohorts :
 
- Cohort 4: solid tumours including non-small-cell lung cancer (NSCLC), bladder cancer, melanoma, gastric cancer, ovarian cancer, triple-negative breast cancer (TNBC), and renal-cell cancer (RCC)- Cohort 5: Tumours with high tumour-mutational burden (TMB), excluding those with high microsatellite instability (MSI-high)- Cohort 6: Refractory squamous cell cervical, anal, and skin tumours.- Cohort 7: Recurrent human papillomavirus (HPV)-positive, or HPV-negative (per local testing), vaginal or vulvar squamous cell carcinoma (VSCC), not amenable to surgery.	

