If DLTs are observed in the first two consecutive patients of a previously untested dose level, subsequent enrolment to that cohort will be stopped. The BLRM will be re-run to confirm that the dose level still fulfils the EWOC principle. Based on this information, the SRC will evaluate whether the next patients will be enrolled at the same dose level, or if they will be enrolled at a lower dose level.

The SRC may recommend stopping the dose-finding phase after the criterion for MTD (Section 7.1) is fulfilled. Further patients may be included to confirm this MTD estimate, i.e., to confirm that the EWOC criterion is still fulfilled. If no DLT is observed at a dose at which the efficacy is considered sufficient, the SRC may decide to include an additional number of patients at the same dose level and to declare this dose as the recommended dose for further development (RP2D). The SRC can declare any dose that fulfils the EWOC criterion as RP2D, independent of the MTD estimate.

Following determination of the MTD and/or RP2D from the Phase Ia portion, separate cohorts of approximately 30-40 patients each will be conducted in patients with select advanced solid malignancies including tumours with specific histology/tumour types and/or specific genetic profiles as specified in the following cohorts:

- Cohort 4: Solid tumours including NSCLC, bladder cancer, melanoma, gastric cancer, ovarian cancer, triple-negative breast cancer, and renal-cell cancer
- Cohort 5: Tumours with high TMB excluding those with high microsatellite instability (MSI-high)
- Cohort 6: Refractory squamous cell cervical, anal, and skin tumours
- Cohort 7: Recurrent human papillomavirus (HPV)-positive, or HPV-negative, vaginal or vulvar squamous cell carcinoma (VSCC)

The Phase Ib portion of the trial will further evaluate the safety, tolerability, efficacy, PK profile, and biomarkers of BI 754091.

The analysis of the squamous cell tumour cohort (Cohort 6) and the VSCC cohort (Cohort 7) will follow a two-stage approach.

The interim analysis for Cohort 6:

- Squamous cervical and/or anal cancer, Stage 1 will include 10 treated patients.
- Squamous skin tumours, Stage 1 will include 10 treated patients.

The interim analysis for Cohort 7:

- Vaginal or VSCC, Stage 1 will include 20 treated patients.

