Based on the interim analyses results, the sponsor will determine if recruitment into these tumour groups will continue or be terminated (recruitment does not have to pause while interim analysis is conducted). More details on the interim analyses are specified in Section 7.4. The sponsor reserves the right to terminate recruitment in any of the tumour groups if the recruitment target is not met. Patients who are already enrolled may continue in the trial regardless of recruitment termination of their cohort.

Patients will continue treatment with BI 754091 until disease progression (PD) according to the Response Evaluation Criteria in Solid Tumours (RECIST) and the Guidelines for Response criteria for use in trials testing immunotherapeutics (iRECIST) (R17-0923, withdrawal of patient consent, an unacceptable toxicity occurs, or 1 year of treatment is completed, whichever occurs first but no longer than 31 August 2023. Patients will be allowed to stay on treatment in the case of initial radiological PD, if the Investigator feels that

it is in the patient's best interest. In addition, patients without PD may stay on trial after 1 year on a case-by-case basis after discussion with the Medical Monitor and the sponsor, but no longer than 31 August 2023. After this date treatment with the ezabenlimab will no longer be available.

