7.4 INTERIM ANALYSES

The sponsor will continuously monitor the safety. The dose-escalation design dictates that the sponsor and the SRC perform regular safety evaluations. These evaluations will be unblinded to dose.

If considered necessary, as soon as the MTD is determined, an evaluation of the safety aspects will be performed. Results of this evaluation will be documented and archived. If applicable, such an analysis will be defined in more detail in the TSAP.

No formal interim analysis of PK data is planned. However, an exploratory analysis of PK will be done after patients in Cohort 1 complete Cycle 1 and once patients in Cohort 2 complete Cycle 1. Further exploratory analyses of PK might be performed if considered reasonable.

Exploratory PK analyses will be based on planned sampling times, if information on actual times should not be available. The results of these evaluations will be preliminary and may be subject to change, as these do not involve a formal database lock. No interim report will be written for exploratory PK analyses. If medically justified, further or fewer exploratory PK analyses may be performed.

Interim efficacy analyses are planned for selected groups of patients (defined in Section 3.1) in the Phase Ib portion of the trial. Because of the expected challenge in recruiting these patients, the two-stage design is planned to stop further recruitment of the specific patient group if the defined efficacy boundary (see Table 7.4: 1) is not met at the first stage. Interim efficacy analyses were not deemed necessary for the TMB high cohort 5 as recent literature already demonstrates an association between high TMB and better response rates for patients taking immune checkpoint inhibitors (R18-1492).

The interim analyses for Cohort 6 will be conducted when:

- 10 patients with squamous cervical and/or anal cancer have been treated, and the 10th patient has been on treatment for ~3 months.
- 10 patients with squamous skin tumours have been treated, and the 10th patient has been on treatment for ~3 months.

The interim analysis for Cohort 7 will be conducted when 20 patients with vaginal or VSCC have been treated, and the 20th patient has been on treatment for ~3 months.

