It has been calculated that with an earlier interim point, the probabilities of false early stopping or observing a false positive/negative result at the final analysis will be too high. With a later interim point, the false positive, false negative and false early stopping probabilities will be improved, but the scale of improvement is not that meaningful.

- Literature on preliminary data of nivolumab and pembrolizumab ([R17-3902](#); [R17-3903](#); [R17-3822](#)) showed ORR ranges from 13% to 24% in patients with squamous cervical and anal tumours. Therefore, an underlying ORR of 25% is assumed. The probability of observing zero responders out of 10 and stopping at interim is 6%, and the probability of observing $\geq 20\%$ ORR at final analysis is 77%. If the underlying ORR is 5%, the probability of stopping early is 61%, and the false positive probability of observing $\geq 20\%$ ORR at final analysis is almost 0.
- It was shown in Chalmers ZR et al, 2017 ([R17-3824](#)) that the population with squamous skin cancer had very high proportion of patients with high TMB (~70%). Therefore, the clinical benefit is expected to be similar to patients with high TMB ([R17-3768](#)). Assume the underlying ORR is 50%, the probability of observing < 3 responders out of 10 and stopping at interim is 5%, and the probability of observing $\geq 40\%$ ORR at final analysis is 87%. If the underlying ORR is 20%, the probability of stopping early is 67%, and the false positive probability of observing $\geq 40\%$ ORR at final analysis is 1%.
- Literature on preliminary data from older chemotherapy/targeted agent trials ([R18-2645](#); [R18-2646](#); [R18-2647](#)) and early phase immunotherapy trials ([R18-2650](#); [R18-2651](#)) showed ORR ranges from 13% to 29% in patients with recurrent, inoperable VSCC. Therefore, an underlying ORR of 25% is assumed. The probability of observing 0 or 1 responder out of 20 and stopping at interim is 2%, and the probability of observing $\geq 20\%$ ORR at final analysis is 82%. If the underlying ORR is 5%, the probability of stopping early is 74%, and the false positive probability of observing $\geq 20\%$ ORR at final analysis is almost 0.

Table 7.4: 1 Early stopping criterion and probabilities for the two-stage approach – selected patient groups

Assumed underlying ORR	Total sample size	Stage 1 sample size	Early stopping criterion (observed ORR)	Early stopping prob.	Observed ORR at final	Probability of observed ORR at final

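### The stated enrolment (about 130 in Phase Ib, about 145 in total, cohorts of 30-40) does not match the plan's own two-stage rules, which are expected to give about 157 and 172 at the planning response rates

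*Protocol*

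**What the plan says.** The headline numbers agree with one another. The synopsis gives the total as "Approximately 145 patients, depending on dose-escalation results", with about 15 patients in Phase Ia, and describes the expansion as "4 cohorts of approximately 30-40 patients each". Section 3.1 repeats that "separate cohorts of approximately 30-40 patients each will be conducted". Section 7.1.2 says that Phase Ib "will recruit approximately 130 patients with selected locally advanced or metastatic cancers".

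The design sections give other sizes:

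- **Cohort 6** has two separate interim analyses. Section 3.1 sets stage 1 at 10 patients for cervical and/or anal tumours and, separately, "Squamous skin tumours, Stage 1 will include 10 treated patients". Section 7.4 times the second of these to when "10 patients with squamous skin tumours have been treated, and the 10th patient has been on treatment for ~3 months". Table 7.4:1 gives each group its own total of 30. Section 7.7.2 accordingly lets Cohort 6 run from 20 to 60.
- **Cohort 7** has 20 patients at stage 1 and 40 if it continues (Section 7.7.2, Table 7.4:1).
- **Cohorts 4 and 5** have about 30 each (Section 7.7.2).

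**The concern.** A Cohort 6 of 60, or of 20, is not a cohort of 30-40, and nothing in the protocol reconciles the two statements. The stated 130 can be rebuilt as 30 + 30 + 30 + 40, that is, with Cohort 6 counted as one group of 30 although Table 7.4:1 gives it two. This is an inference, because the protocol never itemises 130. The amendment history fits it: Cohorts 4 to 6 came in at about 30 each with a Phase Ib total of 90, and 90 became 130 when Cohort 7 was added. That history is cited only for how the number seems to have been built.

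The stated patient number is what ethics committees, authorities and anyone planning recruitment or drug supply will read as the number to be exposed. If the drug performs as Section 7.4 assumes, the trial can follow every one of its own rules and still pass that number by a clear margin.

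**Working it through.** **Inputs.** Phase Ia 15 (synopsis, Section 3.1). Cohorts 4 and 5 at 30 each (Section 7.7.2). Stage 1 size, full size and stopping rule from Table 7.4:1. Planning response rates from Section 7.4: cervical/anal 25%, skin 50%, vaginal/VSCC 25%.

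**Reproducing the plan's figures.** With X binomial, the early-stopping probabilities are:

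- cervical/anal: P(X = 0 | 10, 0.25) = 0.0563 (plan: 6%)
- skin: P(X ≤ 2 | 10, 0.50) = 0.0547 (plan: 5%)
- vaginal/VSCC: P(X ≤ 1 | 20, 0.25) = 0.0243 (plan: 2%)

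The probabilities of reaching the final response threshold also reproduce: 77.6%, 87.0% and 81.3%, against 77%, 87% and 82%. Table 7.4:1 is therefore sound, and the problem lies in the headcount. The stated headcount is recovered only as 30 + 30 + 30 + 40 = 130 and 130 + 15 = 145.

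**Nominal range.** Phase Ib runs from 30 + 30 + 20 + 20 = 100 to 30 + 30 + 60 + 40 = 160. Adding 15 gives 115 to 175. Each group that stops early removes 20 patients, so the nominal Phase Ib sizes are 100, 120, 140 and 160.

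**Expected size at the planning rates.** E[N] = stage 1 size + P(continue) × (full size − stage 1 size).

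| Group | P(continue) | E[N] |
|---|---|---|
| Cervical/anal | 0.9437 | 10 + 20 × 0.9437 = 28.9 |
| Skin | 0.9453 | 10 + 20 × 0.9453 = 28.9 |
| Vaginal/VSCC | 0.9757 | 20 + 20 × 0.9757 = 39.5 |

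Cohort 6 is expected at 57.8. Phase Ib is 30 + 30 + 57.8 + 39.5 = 157.3, and the total is 157.3 + 15 = 172.3.

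- Against 130: 27.3/130 = 21% more.
- Against 145: 27.3/145 = 19% more.

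The plan's rounded stopping probabilities lead to the same place: 60 + 28.8 + 29.0 + 39.6 = 157.4.

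**Distribution at the planning rates.** P(160) = 0.9437 × 0.9453 × 0.9757 = 0.870; P(140) = 0.124; P(120) = 0.006; P(100) < 0.001. Phase Ib is nominally 140 or more with probability 99.4%.

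**Other response rates** (cervical/anal, skin, vaginal/VSCC):

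| True rates | Phase Ib | Total | Total vs 145 |
|---|---|---|---|
| 25% / 50% / 25% | 157.3 | 172.3 | +19% |
| 20% / 40% / 20% | 153.1 | 168.1 | +16% |
| 13% / 50% / 13% | 149.0 | 164.0 | +13% |
| 10% / 30% / 10% | 137.5 | 152.5 | +5% |
| 10% / 25% / 10% | 134.7 | 149.7 | +3% |
| 5% / 20% / 5% | 119.8 | 134.8 | −7% |

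The 13% in the third row is the low end of both literature ranges quoted in Section 7.4.

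**The case against.** The strongest reply is that nothing is hidden. Section 7.7.2 already gives 20 to 60 for Cohort 6 and 20 or 40 for Cohort 7, and the headline counts are worded as approximate. They are also the exact midpoints of 100-160 and 115-175, and 30 + 30 + 40 + 30 gives 130 while keeping every cohort within 30-40. Disclosure in Section 7.7.2 does lessen the harm, but it leaves two incompatible statements in one protocol. The midpoint reading needs a Cohort 7 of 30, which the rules do not nominally produce. An approximate figure does not stretch to 19-21%, and it cannot turn 60 into 30-40. The synopsis caveat about dose escalation concerns Phase Ia, whereas the gap arises in Phase Ib.

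A second reply is that the planning rates are favourable. Section 7.4 cites "ORR ranges from 13% to 24% in patients with squamous cervical and anal tumours" and then assumes 25%. It also expects skin tumours to behave like high-TMB tumours, for which Section 7.7.2 plans on 35%. At 13% / 35% / 13% (skin continuation 0.738), Phase Ib is 60 + 25.0 + 24.8 + 35.1 = 144.9 and the total 159.9, about 10% above 145. This stands as a limit on the size of the excess. The planning rates are nevertheless the protocol's own, and a stated size should agree with them.

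Third, the sponsor may end recruitment in a tumour group that misses its target, and Section 7.4 expects recruitment to be hard, so a continuing group may not fill. That is fair. In the other direction, Section 3.1 says "recruitment does not have to pause while interim analysis is conducted", so a group that stops may already have passed its stage 1 size.

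It is also fair that a Cohort 7 of 20 is simply a group that stopped early; the upper end of Cohort 6 is the clearer contradiction. Finally, Phase Ib is descriptive, no test or estimator uses 130 or 145, and this protocol version ends treatment by 31 August 2023. These points reduce the practical weight without making the number right.

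**Conclusion.** The concern holds. The cohort size of 30-40 contradicts Section 7.7.2 directly, without any modelling. The totals of 130 and 145 are not what the design is expected to deliver under its own assumptions: about 157 in Phase Ib and 172 in total, an excess of about 27 patients. They are not impossible, since they lie inside the nominal ranges and would be approached if the response rates were near the low rows of Table 7.4:1.

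The expected sizes assume 30 patients in each of Cohorts 4 and 5, 15 in Phase Ia, continuing groups that fill completely, and stopped groups that end exactly at stage 1. The decision probabilities in Table 7.4:1 are unaffected. This is a correction to make because the stated sample size is wrong as written, although its practical effect at this stage of the trial is modest.

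**What to change.** In the synopsis and Section 3.1, replace the uniform 30-40 per cohort with the actual sizes: Cohorts 4 and 5 about 30 each; Cohort 6 20-60, made up of 10-30 in each of its two tumour groups; Cohort 7 20-40. In Section 7.1.2, restate Phase Ib as nominally 100-160. In the synopsis, restate the total as nominally 115-175. Add that sizes near the upper figures are expected at the planning response rates.

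Also say that the lower figures are nominal, because recruitment may continue while an interim result is awaited (about 3 months after the last stage 1 patient starts), and that the sponsor may end recruitment in a group.

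The cost is a text change and a larger headline number. The design, decision rules and analyses stay as they are, and no patient is added beyond what Section 7.7.2 already allows.
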